**Table 5. Patterns of subjects' disposition identifying Safety and Efficacy Analysis Population/Dataset**

| Analysis Population:            | Analysis dataset:             |                                   |
|---------------------------------|-------------------------------|-----------------------------------|
|                                 | First Part (8 weeks)          | Main Part (24 weeks)              |
| Safety Global            | a + 1 st part of b | 2 nd part of b + c + d |
| Safety Inferential       | -                             | c + d                             |
| Efficacy ITT Global      | -                             | 2 nd part of b + c + d |
| Efficacy ITT Inferential | -                             | c + d                             |

#### **4.2.3 PK/PD Population**

The PK/PD population will be used for exploratory PK/PD analyses. The PK/PD population consists of a subset of the Efficacy Global population and includes all subjects with at least one post-baseline efficacy measurement and an exposure estimate. For subjects assigned to Placebo, exposure will be assumed to be 0. In case of missing PK information for subjects assigned to a starting dose other than Placebo, the subject with missing PK information will be excluded from exposure-efficacy analyses.

#### **4.3 ANALYSIS OF STUDY CONDUCT**

The number of subjects who enroll, discontinue or complete the study will be summarized for the Safety population/dataset by treatment group. Reasons for premature withdrawal from the study and premature withdrawal from treatment will be listed and summarized.

#### **4.4 ANALYSIS OF TREATMENT GROUP COMPARABILITY**

Demographic and baseline characteristics (including age, sex, WASI-II IQ score, SRS-2 total t-score, Vineland™-II 2DC score) and clinically relevant disease characteristics (including background antipsychotics) will be summarized for the Safety population/dataset by treatment group using means, standard deviations, medians and ranges for continuous variables and proportions for categorical variables, as appropriate.

#### **4.5 EFFICACY ANALYSES**

Summary tables and graphs will be provided both for the "Efficacy ITT Global" and for the "Efficacy ITT Inferential" populations, while listings of individual data will be provided for the "Efficacy ITT Global" population only, separately by subjects' patterns (b, c, d).

Inferential statistical analysis will be performed on pooled data from subjects taking balovaptan 10 mg equivalent dose compared with those from the concurrently randomized placebo in the corresponding randomization stage, as identified by the "Efficacy ITT Inferential" population. Multiple endpoints will be analyzed however, due to the exploratory nature of the study, multiplicity will not be statistically adjusted for and the risk of false positive results will be taken into consideration during the interpretation of the results.

The primary efficacy endpoint, the change from baseline of Vineland™-II 2-DC standard score, as well as the secondary endpoints expressed in terms of change from baseline on a continuous scale (namely, Vineland™-II standard scores, PedsQL Scale factors, ABC factors and RBS-R factors) will be analyzed using Mixed Model Repeat Measurements (MMRM) on the overall population of adolescents and children. The MMRM model will include treatment, sex and visit (week) as main effects, individual age and baseline score as covariates, and treatment-by-visit and baseline-by-visit as interaction terms. Visit will be fitted as a repeated effect with an unstructured correlation structure across visits within each subject. All main effects and interactions will be retained in the final model regardless of their statistical significance.

The results of the analysis will be presented as point estimates, 90% confidence intervals and associated p-values for the adjusted mean differences between 10 mg eq balovaptan and placebo after 24 weeks of treatment as well as at intermediate visits.

The main analysis outlined above will be done using a mixed effect model, which can handle missing data without any need to recur to imputation or discarding of data.

The proportion of subjects with ≥6-point improvement in the Vineland™-II 2DC score (clinically meaningful response) will be analyzed using logistic regression. A Generalised Estimating Equations (GEE) model will be fitted including treatment, sex and visit (week) as main effects, age as covariate, baseline-by-visit and treatment-by-visit interactions, with subject fitted as a repeated effect. It will be based on the binomial distribution and thus the link function will be the 'logit'.

The odds ratio will be presented for descriptive purposes along with the corresponding 90% confidence interval and p-value for the comparisons between 10 mg eq balovaptan and placebo after 24 weeks of treatment as well as at intermediate visits.

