4.3 METHOD OF TREATMENT ASSIGNMENT AND BLINDING

Subjects who meet all of the inclusion criteria and none of the exclusion criteria will be stratified by age group and sex and randomized in a 1:1 ratio (10 mg eq:placebo) to receive of 10 mg/day (age adjusted dose equivalent to adult dose) 24 weeks as double-blinded study medication or placebo. The allocation to individual treatment will be implemented using an Interactive (voice/web) Response System (IxRS).

Approximately equal numbers of children (aged 5–12 years) and adolescents (aged 13–17 years) will be enrolled. Additionally, the proportion of female subjects will be limited to a maximum of 20% of the entire study population. Furthermore, stratification will guarantee (for exposure checks purpose, see Section 3.1.3.1) that, in the first 30 children cohort and first 24 adolescent cohort, 10 of the youngest subjects 13-14 years old in adolescent group and approximately 10 of the 5–7 years old in children group will take active treatment. However, if final doses cannot be determined for the subgroup or cohort, and additional subjects are required for dose confirmation to occur, the size of the cohort will increase (see Section 3.1.3.1 for further details). The children’s cohort should contain up to approximately 16 subjects aged between 5 and 7 years old. Subjects from first adolescent and first children cohorts, who stopped treatment in the context of the interim safety and PK decisions, (see Section 3.1.3) will be allowed to re-start in the same treatment arm, according to their original randomization, for an additional 24 weeks in the main study, provided the Investigator can exclude relevant changes in the subject’s general condition (see Section 4.2.1). Unblinding should not occur except in the case of emergency situations. Unblinding will be performed by means of the IxRS.

As per regulatory reporting requirements, Roche will unblind the identity of the study medication for all unexpected serious adverse events that are considered by the Investigator to be related to study drug as per safety reference document(s), i.e., Investigator Brochure [45]. Details of subjects who are unblinded during the study will be included in the Clinical Study Report.

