6. STATISTICAL CONSIDERATIONS AND ANALYSIS PLAN

6.1 DETERMINATION OF SAMPLE SIZE

Prior to Version 6 of the protocol, a sample size of 240 ASD patients (80 per treatment arm) providing evaluable data at Week 24 ensured the study 80% power to detect as statistically significant, at 1-sided 5% significance level, a difference between each active dose and placebo with an effect size of at least 0.4. No adjustment for multiple doses was performed. Considering a withdrawal rate of around 15-20%, it was planned to recruit approximately 300 subjects overall.

In accordance to Version 6 of the protocol, 80 subjects per treatment arm (balovaptan 10 mg eq and placebo) will be required, for a total sample size of approximately 160 subjects with ASD with evaluable data at Week 24. To maintain the number of evaluable subjects, the sample size will be increase to approximately 340 subjects overall.

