### **2.3 DETERMINATION OF SAMPLE SIZE**

Prior to protocol version 6, a sample size of 240 subjects with ASD (80 per treatment arm) providing evaluable data at Week 24 ensured the study 80% power to detect as statistically significant, at 1-sided 5% significance level, a difference between each active dose and placebo with an effect size of at least 0.4. For the Vineland™-II 2DC score, assuming a standard deviation of about 12.5 points, then the effect size of 0.4 corresponds to 5 points. No adjustment for multiple doses was performed. Considering a withdrawal rate of around 15-20%, it was planned to recruit approximately 300 subjects overall.

In accordance to protocol version 6, 80 subjects per treatment arm (balovaptan 10 mg equivalent and placebo) are required, for a total sample size of approximately 160 subjects with ASD with evaluable data at Week 24. To achieve this number of evaluable subjects, the overall sample size in the study since it started is expected to increase to approximately 340 subjects.

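### The 6-point responder GEE has no stated missing-data rule, so its Week 24 odds ratio rests on a stronger assumption than the MMRM of the same score

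*SAP*

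**What the plan says.** SAP 4.5 gives the responder model as "A Generalised Estimating Equations (GEE) model will be fitted including treatment, sex and visit (week) as main effects", with age as a covariate, baseline-by-visit and treatment-by-visit interactions, subject as the repeated effect and a logit link. The Week 24 odds ratio is labelled descriptive but is reported with a 90% confidence interval and a p-value, as are the intermediate visits.

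The section's only statement on missing data concerns the mixed model used for the main analysis, "which can handle missing data without any need to recur to imputation or discarding of data". Nothing equivalent is said for the GEE. An unstructured correlation is specified for the MMRM; none is named for the GEE. SAP section 5 leaves the 2DC uncomputed when either domain score is missing, and responder status is then missing too.

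Under Protocol Appendix 1, Vineland-II has two scheduled post-baseline visits in the double-blind period (Weeks 12 and 24), plus the Early Withdrawal visit. In SAP 3.3 the Week 24 window opens on Day 149; Early Withdrawal visits are not mentioned there. On withdrawal, SAP 2.3 says: "Considering a withdrawal rate of around 15-20%, it was planned to recruit approximately 300 subjects overall". Neither document describes its timing, its causes or any difference between arms.

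**The concern.** The MMRM and the responder model analyse the same score at the same visits under different missing-data assumptions. For a subject seen at Week 12 but not at Week 24, the MMRM uses the Week 12 value in estimating the Week 24 means. With treatment-by-visit and baseline-by-visit terms and an independence working correlation, the GEE's Week 24 odds ratio is in effect a comparison of those still observed. With an exchangeable working correlation the Week 12 responses carry some weight, but this does not give the GEE the MMRM's validity under missing at random.

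The 6-point threshold is the trial's definition of clinically meaningful response (Protocol 3.3.7), and the proportion reaching it is a named secondary objective (SAP 2.1.2). If poor improvers leave one arm more selectively than the other, the odds ratio can show a benefit that does not exist, or hide one that does, while the MMRM stays unbiased.

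**Working it through.** **Inputs from the documents.** "80% power to detect as statistically significant, at 1-sided 5% significance level"; "assuming a standard deviation of about 12.5 points, then the effect size of 0.4 corresponds to 5 points"; "80 subjects per treatment arm (balovaptan 10 mg equivalent and placebo) are required"; 1:1 allocation (Protocol 4.3); 15-20% withdrawal.

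**The plan's own figures, reproduced.**
- n per arm = 2(1.645 + 0.842)² / 0.4² = 77.3, so 78 (plan: 80).
- Power at 80 per arm = Φ(0.4·√40 − 1.645) = Φ(0.885) = 0.812 (plan: 80%).
- 240 / (1 − 0.20) = 300, the earlier recruitment target; 15% would give 283.
- 80 / (1 − 0.20) = 100 randomised per arm, used below.

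The documents give no figure for the responder analysis.

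**Assumptions not in the documents.** No treatment effect; mean change 3 points at Week 12 and 4 at Week 24; SD of change 12.5; Week 12-24 correlation ρ = 0.6 (range 0.4-0.8); all withdrawal after Week 12; log-odds of withdrawal changing by −1 per SD of Week 12 change in the active arm and by 0 on placebo.

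**Hand check of the completer comparison (20% withdrawal, ρ = 0.6).**
1. True responder rate in both arms: 1 − Φ((6 − 4)/12.5) = 1 − Φ(0.16) = 0.436.
2. Active-arm withdrawal probability: w(z) = 1/(1 + exp(1.65 + z)), with z the standardised Week 12 change; the constant gives 20% overall.
3. Rate among active completers: ∫(1 − w(z)) φ(z) [1 − Φ((0.16 − 0.6z)/0.8)] dz / 0.80 = 0.476.
4. Odds ratio: (0.476/0.524)/(0.436/0.564) = 1.175; log 0.1613.
5. SE with 80 per arm: √[1/(80·0.476·0.524) + 1/(80·0.436·0.564)] = 0.3177.
6. One-sided rejection: 1 − Φ(1.645 − 0.1613/0.3177) = 12.8%.

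The same steps give 10.6% at 15% withdrawal and 16.2% at slope −1.5.

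**Simulation of the GEE itself** (3,000 trials per scenario, Monte Carlo SE about 0.4 points at 5%; 20% withdrawal and ρ = 0.6 unless stated). One-sided rejection under the null:

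Where the GEE holds its level:
- Withdrawal completely at random: 5.6%.
- Dependent on baseline only: 5.2%.
- Dependent on Week 12 change, same mechanism in both arms: 5.0% (slope −1), 5.4% (slope −2), odds ratio 1.00.

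Where it does not:

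| Scenario | Independence | Exchangeable |
|---|---|---|
| Same slope, withdrawal 25% vs 15% | 8.4% | 6.0% |
| Slope −1, active arm only | 12.9% (OR 1.18) | 7.5% (OR 1.06) |
| Opposite slopes (extreme case) | 27.0% (OR 1.41) | 11.3% (OR 1.14) |

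For the active-only case, independence gives 10.7% at 15% withdrawal and 8.9-16.8% over ρ = 0.4-0.8. Two-sided non-coverage of the 90% interval moves less: 11.5-17.8% over that range with independence and 9.8-11.9% with exchangeable, against 10%. If the placebo arm lost its poor improvers instead, the bias would favour placebo.

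The MMRM stayed at 4.6-6.2% throughout. An inverse-probability-weighted GEE gave 4.3-5.4% in every null scenario. Counting withdrawals as non-responders did not help: 12.6% in the active-only case.

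**Timing.** If half the withdrawals precede Week 12 at random (a further assumption), the completer test rejects 8.7-10.1% at 20% withdrawal and 7.7-8.6% at 15% (slopes −1 to −1.5).

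**Check of the proposed fix.** In a separate simulation of the active-only case, completers rejected 12.2% and multiple imputation of the continuous score 3.4%. With random withdrawal and a true 5-point effect, power was 65.9% with imputation and 62.5% for completers.

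**The case against.** The strongest case against is that this is a secondary odds ratio, labelled descriptive, in an exploratory study. SAP 4.5 declines multiplicity adjustment and says false-positive risk will be weighed in interpretation. No sample size or decision rule rests on this p-value. That stands: no controlled error rate is breached. It does not make a biased estimate or interval informative, and a p-value will be printed beside it.

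Four further objections limit the size:
- The available-case reading comes from the SAP's silence. That is fair, but it is the natural reading of a GEE with no other rule.
- Inflation needs withdrawal that depends on outcome differently in the two arms, in mechanism or rate. The documents give no sign of this. They do not rule it out either, which is why a rule should be fixed in advance.
- A subject who leaves before Week 12 without a usable score gives the MMRM no post-baseline 2DC either, so the MMRM has no advantage there.
- Early Withdrawal scores from Day 149 would fall in the Week 24 window and reduce the missing fraction. Earlier scores cannot: Days 107-148 fall in the Week 18 range, where no Vineland-II is scheduled.

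A reader might also attribute any conflict between the GEE and the MMRM to missing data. Much of it comes from dichotomising: with a true 5-point effect and purely random withdrawal, the MMRM was significant and the GEE was not in 21.4% of simulated trials.

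**Conclusion.** The concern holds in a conditional form. The responder GEE needs withdrawal to be random or to depend only on arm, visit, sex, age and baseline, which is stronger than the missing-at-random assumption behind the MMRM. If withdrawal after Week 12 depends on Week 12 change in one arm only, at 20% withdrawal and correlation 0.6, one-sided rejection under the null is about 12-13% (independence) or about 7.5% (exchangeable). It is lower if part of the withdrawal precedes Week 12 or if Early Withdrawal scores fall in the Week 24 window. The gap between the two figures shows that the unstated working correlation affects the result.

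Two stronger readings are tempting and are not supported. A reader might infer that the GEE is valid only under completely random withdrawal; dependence on baseline alone did no harm. A reader might also infer that the plan as it stands inflates the false-positive rate; with the same mechanism and rate in both arms there was no inflation, and the documents do not describe the withdrawal pattern. The change is a worthwhile, cheap improvement and does not correct an error in the primary analysis.

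**What to change.** Add a paragraph to SAP 4.5:
- Multiply impute the continuous 2DC at Weeks 12 and 24, separately by arm, under the missing-at-random assumption of the MMRM.
- Use Early Withdrawal scores in the window where they fall, and say how one in the Week 18 range is handled.
- Dichotomise each completed dataset at 6 points, and at 4 and 8 for the exploratory thresholds.
- Fit the logistic model with the same covariates and combine by Rubin's rules.
- Report the observed-case GEE alongside, with its working correlation stated.

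The cost is one paragraph and modest programming; no new data are needed. The downside is reliance on the same missing-at-random and normality assumptions as the primary analysis. Disagreement with the MMRM that comes from dichotomising will remain.

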#### **Change from baseline in severity of clinical impressions as measured by CGI-S**

The proportion of subjects with at least 1-point decrease (i.e. improvement) from baseline on CGI-S will be analyzed using logistic regression. A GEE model will be fitted including treatment, sex and visit (week) as main effects, age and baseline CGI-S as covariates, baseline-by-visit and treatment-by-visit interactions, with subject fitted as a repeated effect. It will be based on the binomial distribution and thus the link function will be the 'logit'.

The odds ratio will be presented for descriptive purposes along with the corresponding 90% confidence interval and p-value for the comparisons between 10 mg eq balovaptan and placebo after 24 weeks of treatment as well as at intermediate visits.

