4.6.1.10.9 Clinical Global Impression—Severity (CGI-S) and Improvement (CGI-I)

The CGI rating scales are tools used to evaluate both the severity of illness and change from baseline [39]. The CGI-S reflects the rater’s impression of the subject’s current autism severity on a 7-point scale ranging from no symptoms (1) to very severe symptoms (7). The CGI-I is used to assess the clinical change as compared to symptoms at baseline using a 7-point scale, ranging from very much improved (1) to very much worse (7). For this study modified versions will be used [40, 41].

Whenever possible, for any individual, these assessments should be done by the same rater throughout the study.

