### **2.1.2 Secondary Objectives**

The secondary objective of this study are as follows:

- To evaluate the efficacy of treatment with balovaptan 10 mg equivalent vs. placebo on:
  - Change from baseline on the Vineland™-II Composite standard score after 12 weeks and 24 weeks of treatment
  - Change from baseline in the Vineland™-II Communication, Socialization and Daily Living Skills domain standard scores after 12 weeks and 24 weeks of treatment
  - Proportion of subjects with ≥6-point improvement in the Vineland™-II 2DC score (clinically meaningful response)
  - Change from baseline in severity of clinical impressions as measured by CGI-S (Clinical Global Impressions-Severity) and OACIS-S (Ohio Autism Clinical Impressions Scale-Severity) after 12 weeks and 24 weeks of treatment
  - Improvements in clinical impressions as measured by CGI-I (Clinical Global Impressions-Improvement) and OACIS-I (Ohio Autism Clinical Impressions Scale-Improvement) after 12 weeks and 24 weeks of Treatment
  - Change from baseline in patient- or parent-reported Pediatric Quality of Life (PedsQL) v4.0 Generic Core Scale after 12 weeks and 24 weeks of treatment
  - Change from baseline in the Vineland™-II Composite standard score in adolescents and children independently after 12 weeks and 24 weeks of treatment
  - Change from baseline on the Vineland™-II 2DC score after 12 weeks of treatment
- To evaluate safety and tolerability of 24 and up to 76 weeks of treatment with balovaptan
- To evaluate the pharmacokinetics and exposure-response relationships of balovaptan and its metabolites, if appropriate

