### **2.2.2 Secondary Efficacy Endpoints**

The secondary efficacy endpoints are as identified in the list of secondary objectives (see Section 2.1.2)

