#### **Improvements in clinical impressions, as measured by CGI-I scores**

The proportion of subjects with a value of at least 2 (i.e., "Much improved" or better) on CGI-I will be analyzed using logistic regression applying the same model above described for CGI-S.

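### CGI-S is a change-from-baseline endpoint, but the SAP models only a 1-point responder cut; a full-scale analysis of change should be added beside it

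*SAP*

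**What the plan says.** SAP 2.1.2 lists among the secondary objectives, at 12 and 24 weeks, "Change from baseline in severity of clinical impressions as measured by CGI-S (Clinical Global Impressions-Severity" (the same item covers OACIS-S). SAP 2.2.2 defines no separate endpoints: "The secondary efficacy endpoints are as identified in the list of secondary objectives". CGI-S therefore enters as a change from baseline, and no CGI-S responder endpoint is listed. Protocol 4.6.1.10.9 describes the scale as the rater's impression of "current autism severity on a 7-point scale ranging from no symptoms (1) to very severe symptoms (7".

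SAP 4.5 sends to the MMRM "the secondary endpoints expressed in terms of change from baseline on a continuous scale" and names them: Vineland-II, PedsQL, ABC and RBS-R. CGI-S is not in that list. Under its own subheading, which still refers to change from baseline, the plan is: "The proportion of subjects with at least 1-point decrease (i.e. improvement) from baseline on CGI-S will be analyzed using logistic regression". The model is a logistic GEE with treatment, sex, visit, age, baseline CGI-S and the two visit interactions. It yields an odds ratio, labelled descriptive, with a 90% interval and a p-value.

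For CGI-I the objective is worded differently: "Improvements in clinical impressions as measured by CGI-I (Clinical Global Impressions-Improvement) and OACIS-I". Its analysis is one cut at much improved or better, "applying the same model above described for CGI-S".

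Protocol 6.6 names no CGI model. It plans frequency tables of raw values and of changes for all efficacy data.

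**The concern.** The endpoint is a change on a 7-level scale, but the modelled quantity is a yes/no at one threshold. A subject who worsens by 2 points and one who stays the same are both non-responders; gains of 1 and 3 points are both responses. Entry requires CGI-S of at least 4 (Protocol 4.2.2), so subjects who start at 4 to 6 have room to worsen, and the model cannot see whether they do.

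At stake is what the report can say about a listed secondary endpoint. It would have an adjusted odds ratio for response, but no adjusted estimate or interval for change. An effect through less worsening, or through larger gains among subjects who improve anyway, would be visible only in tables. The SAP handles its primary scale more fully: Vineland-II 2DC has an MMRM on change and also a responder analysis, and the latter is listed as an objective of its own. CGI-S has only the second kind of analysis.

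**Working it through.** **1. The plan's own figure.** SAP 2.3 states 80 evaluable subjects per arm, 80% power, one-sided 5%, effect size 0.4 (5 points with SD 12.5 on Vineland-II 2DC). Required n = 2(1.645 + 0.842)²/0.4² = 77.3, so 78 per arm. With 80 per arm, power = Φ(0.4·√(80/2) − 1.645) = Φ(0.885) = 81.2%. The figure reproduces. It belongs to the primary endpoint; the documents give no rate, power or sample size for CGI-S.

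**2. Assumed inputs.** CGI-S change is grouped as 2 or more points better / 1 better / same / worse. All placebo distributions below are assumptions. Arms have 80 subjects and tests are one-sided 5%. Powers are simulated (20,000 runs) for one visit without covariates or missing data: the cut as two proportions, the ordered scale by Wilcoxon, and a t-test on the category scores as a simple proxy for an MMRM.

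**3. Information kept by the cut under proportional odds.** The information on the log odds ratio is N·r(1−r)/4 for the cut and N(1−Σp³)/12 for the ordered scale, where p are the category shares averaged over arms and r is the average share of responders. The ratio is

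RE = 3r(1−r)/(1−Σp³).

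Worked case: placebo 5/25/60/10%, common odds ratio 2.0. The placebo cumulative shares 0.05, 0.30, 0.90 become 0.095, 0.462, 0.947 on active. The averaged shares are 0.073, 0.308, 0.543, 0.076, and r = (0.300 + 0.462)/2 = 0.381. Then 3 × 0.381 × 0.619 = 0.707, and 1 − (0.0004 + 0.0293 + 0.1600 + 0.0004) = 0.810, so RE = 0.87.

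**4. Six assumed placebo distributions, odds ratio 2.0.**

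| Placebo (%) | Responders, placebo to active (%) | RE | Power, cut (%) | Power, ordinal (%) | Power, mean score (%) |
|---|---|---|---|---|---|
| 2/13/75/10 | 15 to 26 | 0.79 | 53.7 | 62.1 | 60.7 |
| 5/25/60/10 | 30 to 46 | 0.87 | 66.4 | 72.5 | 71.5 |
| 5/25/68/2 | 30 to 46 | 0.94 | 67.3 | 70.3 | 68.6 |
| 10/35/45/10 | 45 to 62 | 0.85 | 69.4 | 76.2 | 75.7 |
| 15/40/35/10 | 55 to 71 | 0.79 | 67.2 | 76.7 | 76.0 |
| 5/15/60/20 | 20 to 33 | 0.74 | 61.1 | 72.1 | 71.2 |

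Over odds ratios 1.5 to 2.5 for the same six distributions, RE runs from 0.69 to 0.95.

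**5. Effects that are not a uniform shift.**

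| Placebo to active (%) | Meaning | Power, cut (%) | Power, ordinal (%) | Power, mean score (%) |
|---|---|---|---|---|
| 5/25/50/20 to 5/25/65/5 | only less worsening | 5.1 | 36.4 | 36.7 |
| 5/25/60/10 to 20/10/60/10 | only larger gains | 5.2 | 14.1 | 31.1 |
| 5/25/60/10 to 5/40/45/10 | only unchanged to improved | 61.3 | 45.0 | 36.7 |
| 5/25/60/10 to 5/40/35/20 | more responders, but also more worsening | 61.5 | 16.8 | 10.8 |

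In the first two rows the share of responders is equal in both arms, so the cut rejects at its error rate. In the third the effect lies exactly at the threshold and the cut is the better test. In the fourth the cut favours active at the same rate as in the third although the share who worsen doubles.

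**The case against.** The strongest reply is that the SAP follows its own rule. It reserves the MMRM for continuous scales, CGI-S is a single 7-level rating, and the responder proportion, adjusted for baseline CGI-S and set out under a change-from-baseline subheading, is a prespecified summary of change. The odds ratio is labelled descriptive, the trial is called exploratory, multiplicity is not adjusted, and the tables will show who worsened. Most of this stands, and it is why the point is minor. It does not supply an adjusted estimate of change. If equal spacing is the worry, an ordinal model answers it.

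A reader might infer more than the documents support:

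- **That CGI-S alone was left out of the MMRM.** It was not. OACIS-S, also a secondary change endpoint, and the exploratory CaGI severity change (SAP 2.2.3) are missing from the list too, and SAP 4.5 names no model for OACIS-S at all.
- **That CGI-I has the same mismatch.** Its objective speaks of improvements, and a much-improved cut answers that. The cut can lose more information there (RE 0.37 to 0.82 under assumed distributions), but refitting CGI-I is a preference and at most an optional sensitivity analysis.
- **That the cut always costs power, and so should be replaced.** The third row of step 5 shows the reverse.
- **That CGI is the main check on the caregiver-informed primary scale.** The documents do not say so, and OACIS is clinician-completed as well.
- **That nothing beyond the cut could ever be modelled.** SAP 4.5.1 applies an MMRM to subgroup analyses of efficacy data without saying whether CGI-S is included. That is unclear rather than absent, and it is not the main analysis.

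**Conclusion.** The point holds as a low-cost improvement. The listed CGI-S endpoint is change from baseline; the only model planned for it in the main analysis is a 1-point responder cut, so change itself, including less worsening, is reported only descriptively.

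The size is modest under a uniform shift: the cut keeps roughly 70 to 95% of the ordinal information. At an odds ratio of 2.0 and 80 per arm, the power gap is 3 to 11 percentage points (67.3 against 70.3 at the least, 61.1 against 72.1 at the most). It is large if the effect lies only away from the threshold, and it reverses if the effect lies only at the threshold. All of this rests on assumed distributions and single-visit comparisons. The mismatch between endpoint and model does not depend on them. The primary endpoint and its sample size are untouched.

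**What to change.** In SAP 4.5, under the CGI-S subheading, add an analysis of CGI-S change from baseline on the full scale, reported at Weeks 12 and 24. Choose one of two forms and state it before the database lock described in SAP 2.4:

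- the MMRM already specified in SAP 4.5, with CGI-S added to its list of endpoints; or
- a cumulative-logit GEE with the covariates already listed for the CGI-S responder model, and a rule written in advance for collapsing sparse extreme levels.

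Keep the 1-point responder odds ratio beside it, and tabulate the share who worsened by arm. Say in SAP 4.5.1 whether the subgroup MMRM covers CGI-S. Leave the CGI-I responder analysis as it is; an ordinal CGI-I model is optional.

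The cost is one extra model on data already collected, with no new visits or subjects. The MMRM treats the seven levels as equally spaced, and the ordinal model assumes proportional odds and may be unstable with few subjects in the extreme levels. Since either the full-scale analysis or the cut can be the more sensitive, depending on where the effect lies, both should be reported whatever they show.
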